--	--

	
Description of the monitoring process
 
The remote monitoring process will be described by:
 
 
• The number and / or rate of alerts generated by the tool depending on the severity level of the alert.
 
• The nature and number of actions implemented and interventions carried out.
 

RESEARCH DESIGN	Single-center, prospective cohort pilot study evaluating the feasibility of a online remote monitoring tool during the care of patients over 65 years of age being medically treated for cancer.
INCLUSION CRITERIA	
 
1. Patients 65 years of age and over.
 
2. Histologically proven cancer: breast, lung, ovary, prostate, bladder, kidney, ENT, colon-rectum, melanoma, sarcoma, lymphoma, myeloma, or myelodysplastic syndrome.
 
3. Included before starting medical treatment (chemotherapy, hormone therapy, targeted therapy, immunotherapy or combination).
 
4. Informed consent dated and signed.
 
5. Patients affiliated with a French social security scheme in accordance with the French law on biomedical research (Article 1121-11 of the French Code of Public Health).
 

NON INCLUSION CRITERIA	
 
1. Life expectancy less than 12 months.
 
2. Patient declining to use a tablet, computer, smartphone or the Internet.
 
3. Patient not knowing how to read and understand French.
 
4. Technical impossibility of connecting to the Internet in the patient's living area.
 
5. Patient already included in this study or in another study evaluating a remote monitoring system.
 

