
SIZE OF STUDY
	
The primary endpoint is the proportion of patients who completed at least 9 questionnaires at 3 months: 6 weekly toxicities / clinical symptoms questionnaires (20 items including 7 mandatory) + 2 EORTC QLQ-C30 quality of life questionnaires (30 items, mandatory scores for the 5 functional scales + the overall QOL) + 1 questionnaire evaluating the benefit of the treatment perceived by the patient (3 items, 1st question mandatory).
 
Based on the results of other feasibility studies on remote monitoring in oncology (SENTINEL (Denis et al., 2014), STAR (Judson et al., 2013) and e-DomSanté1 (Quénel-Tueux et al., 2018)), we will consider the use of our online tool for the remote monitoring of elderly patients with cancer as feasible if 75% of the patients included and having started medical

	
treatment against cancer answer all the questionnaires defined in the primary endpoint criterion. The inclusion of 30 eligible and evaluable patients will allow us to estimate this rate of 75% of patients who answered all the questionnaires (9 in total) with a 95% confidence interval on a bilateral basis of (55.6% - 88.2%). The confidence interval was calculated using Wilson's method with continuity correction. Estimating that 10% of patients will not be eligible / evaluable, we estimate that 33 patients should be included.

RESEARCH DURATION	
Duration of the inclusion period: 24 months  Duration of participation of each participant: 6 months  Total duration of research: 30 months

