STATISTICAL ANALYSIS	
Analysis populations
 
 
• Eligible population: all patients included with no major deviations from the eligibility criteria.
 
• Eligible and assessable population: eligible patients who started medical treatment (chemotherapy, hormone therapy, targeted therapy, immunotherapy or combination).
 
 
Statistical analyses:
 
 
• The primary endpoint will be calculated from the eligible and assessable population.
 
• The proportion of patients who completed 9 questionnaires at three months will be calculated as follows: number of eligible and assessable patients who completed the 9 questionnaires at 3 months divided by the number of eligible and assessable patients. The proportion will be reported with its 95% confidence interval (binomial law).
 
• The secondary endpoints will be calculated from the eligible and assessable population as for the primary endpoint.
 
• The scores of the questionnaires (continuous variables) will be described on the basis of means (+/- standard deviation) if the normality hypothesis is satisfied, and failing that, on the basis of other descriptive statistics (median, range, quartiles).
 
• The scores can be categorized according to the thresholds described in the literature. For each questionnaire, the proportion of patients with a score above or below the predefined threshold will then be reported with its 95% confidence interval (binomial law).
 
• The quantitative variables will be described from the mean and the standard deviation if the assumption of normality is respected, failing other descriptive statistics will be used (minimum, maximum, median and quartiles).
 
• The qualitative variables will be described on the basis of the numbers and associated frequencies, expressed as a percentage (%).
 
 
For each variable, the number of missing data will be described. Whenever possible, the reasons will be documented to assist the interpretation of results.

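### The 75% feasibility rule and the primary analysis differ by an undefined eligibility filter, so a treated patient found unable to connect after inclusion could leave the denominator

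*Combined protocol and SAP*

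**What the plan says.** All the relevant text is in the Summary.

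- **Size of study, decision rule.** The tool will be considered "as feasible if 75% of the patients included and having started medical" treatment complete all the questionnaires of the primary endpoint. This sentence has no eligibility condition.
- **Size of study, next sentence.** "The inclusion of 30 eligible and evaluable patients will allow us to estimate this rate of 75% of patients who answered all the questionnaires". Here the same 75% is attached to eligible and evaluable patients. The section then adds: "Estimating that 10% of patients will not be eligible / evaluable, we estimate that 33 patients should be included".
- **Statistical analysis, Analysis populations.** The eligible population is "all patients included with no major deviations from the eligibility criteria". The eligible and assessable population is the part of it that started medical treatment. The primary endpoint is a fraction with that population as its denominator.
- **Non inclusion criteria.** Criterion 2 is "Patient declining to use a tablet, computer, smartphone or the Internet". Criterion 4 begins "Technical impossibility of connecting to the Internet" and refers to the area where the patient lives.

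The Summary does not say what makes a deviation major, when or by whom this is judged, or on what information. It does not say how to treat a tool-related problem found after inclusion. It plans no analysis that keeps all included patients who started treatment.

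**The concern.** The primary result is a proportion that measures whether older patients can use an online tool. Some of the eligibility criteria describe reasons why such a tool fails. If a patient is included, starts treatment, and then proves unable to connect from home, the decision rule as worded counts a failure. Under the analysis definition the same patient can be classed as a major eligibility deviation and disappear from both numerator and denominator.

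A patient removed for that reason is very likely a non-completer, so removal for that reason pushes the rate up. The rule compares a point estimate with 75% in about 30 patients, so one such decision, possibly taken after completion is known, could settle the study's conclusion. The plan does not say which denominator governs that conclusion.

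**Working it through.** **1. Inputs, all from the Summary.** The threshold is 75%, the planned analysed number is 30, the allowance for patients not eligible or evaluable is 10%, and planned inclusion is 33 (Size of study). The analysed population has no major eligibility deviation and has started treatment (Statistical analysis).

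**2. The plan's own figures.** The stated interval is 55.6% to 88.2%, by Wilson's method with continuity correction. With p = 0.75, q = 0.25, n = 30, z = 1.96:

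- lower = [2np + z² − 1 − z√(z² − 2 − 1/n + 4p(nq + 1))] / [2(n + z²)] = (47.84 − 10.24) / 67.68 = 55.55%
- upper = [2np + z² + 1 + z√(z² + 2 − 1/n + 4p(nq − 1))] / [2(n + z²)] = (49.84 + 9.86) / 67.68 = 88.21%

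The interval reproduces. For the allowance, 30 × 1.10 = 33 gives the stated number; 30 / 0.90 = 33.3 would round up to 34. The one-patient difference does not matter here.

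**3. What separates the two denominators.** Both leave out patients who never start treatment. The only difference is the group of included, treated patients removed for a major eligibility deviation. Call their number k. The plan's allowance suggests a total of about three removals (33 − 30), but this total also covers patients who never start treatment. So k = 3 is a worst case.

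**4. Effect on the verdict.** Let x be the completers among 30 analysed, and assume that the k removed patients are all non-completers. The analysis rate is x/30. The rate on the decision rule's wording is x/(30 + k).

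| Completers x | x/30 | x/31 (k = 1) | x/32 (k = 2) | x/33 (k = 3) |
|---|---|---|---|---|
| 22 | 73.3% | 71.0% | 68.8% | 66.7% |
| 23 | 76.7% | 74.2% | 71.9% | 69.7% |
| 24 | 80.0% | 77.4% | 75.0% | 72.7% |
| 25 | 83.3% | 80.6% | 78.1% | 75.8% |

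The fewest completers that reach 75% are 23 of 30, 24 of 31, 24 of 32 and 25 of 33. So:

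- at 23 completers, one added-back patient changes the verdict;
- at 24, three are needed;
- with 22 or fewer, the result is below 75% on every denominator;
- with 25 or more, it is above 75% on every denominator.

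**5. How likely the sensitive range is.** If the true rate is the plan's 75%, the binomial probability of 23 completers of 30 is 16.6% and of 24 is 14.5%, together 31.2% before rounding. Assuming true rates of 70% and 80% instead, the probability of 23 or 24 is 20.5% and 33.3%. These are chances of landing in the range. A change of verdict also requires treated non-completers to have been removed.

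**6. The direction depends on who is removed.** A major deviation could concern any criterion, and such a patient might complete everything. With two completers added back, 22/30 = 73.3% becomes 24/32 = 75.0%, which moves the other way. The upward bias holds for removals caused by tool problems, not for eligibility exclusions in general.

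**The case against.** The strongest reply is that the plan has one denominator and one loosely worded sentence. Immediately after the rule, Size of study ties the 75% to eligible and evaluable patients, and Statistical analysis writes the fraction out for that population. This is a fair reading and may well be the intended one. It does not close the gap, because both wordings stand in one paragraph and nothing says which decides feasibility.

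A reader might also infer that the plan drops patients who would not use the tool. The documents do not support that. Non-inclusion criteria ordinarily apply at inclusion, and being assessable requires only that treatment has started, with no minimum login or completion. A patient who was willing at inclusion and later stopped stays in the denominator as a failure. Removing that patient would need a reclassification that the plan neither provides for nor forbids. The connection route is more plausible, because a home without a workable connection may be discovered late yet fit criterion 4. It too is narrowed: the Study procedure section mentions equipment lent for the study (a tablet and/or a 3/4G key), and software failures are recorded as secondary outcomes, not as grounds for exclusion.

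Two further points stand. Excluding patients with major eligibility deviations is defensible in a single-arm pilot if it is judged on facts known at inclusion. And with a planned interval of 55.6% to 88.2%, rates of 76.7% and 74.2% are not statistically distinguishable; any point threshold at this size can turn on one patient. That limits the meaning of a changed verdict, but it is no reason to leave the denominator open.

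**Conclusion.** The concern holds in a limited form. The decision rule and the primary analysis differ by an eligibility filter whose key term is undefined and which overlaps with reasons for tool failure. An included, treated patient whose connection problem appears after inclusion could be removed instead of counted as a non-completer, which would raise the feasibility rate.

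With 30 analysed and up to three treated non-completers added back, the verdict changes only at 23 completers (one patient is enough) or at 24 (all three are needed). This assumes that the removed patients had started treatment and did not complete.

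It would go too far to say that the plan sets two deliberately different denominators, that it removes non-users, or that eligibility exclusions must bias the rate upward. This is an ambiguity in the primary analysis that should be settled before the data are analysed.

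**What to change.** State one denominator for the 75% verdict, in the same words in Size of study and Statistical analysis. The preferable choice is the decision rule's own: all included patients who started medical treatment.

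If the eligibility filter is kept:

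- judge major deviations only on information available at inclusion, by someone unaware of questionnaire completion;
- count refusal to use the tool, or failure to connect, found after inclusion as non-completion.

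Report the rate on the other denominator as a sensitivity analysis, and list each treated patient who differs between the two, with the reason. A patient enrolled in error who could not read French (criterion 3) should be listed as an enrolment error and not described as a failure of the tool.

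The cost is a few sentences and one extra proportion. No new data or patients are needed. The downside is that the reported rate may be slightly lower.
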